# 10.4 Cardiac Monitoring

Minor ECG changes are expected following romidepsin administration (refer to current Investigator's Brochure). Cardiac assessments must be performed for all study patients. The treating investigator must perform the primary assessment and is responsible for the cardiac safety of the patients.

# 10.5 Cardiac Alert Findings

In the event of an alert finding, the individual decision about a delay of administration, dose reduction, or withdrawal from the study will be made by the Investigator (in association with local cardiologist, if preferred). All alerts must be confirmed via manual read of the patients ECG; the machine reading alone is not adequate. The following findings are considered to be cause for alert and if they occur, should be reported as AEs or SAEs, as appropriate:

- QTc or QTf is ≥ 500 msec:
  - Either QTc or QTf formulas can be used; the lesser of the two values will be recorded.
  - If the patient has a known incomplete or complete right bundle branch block (RBBB) or left bundle branch block (LBBB) a change in QTc/QTf of > 60 msec from the post antiemetic ECG will be used as criteria for and adverse event and would be graded as a grade 3 adverse event.
  - If the patient has a single or dual chamber pacemaker a change in QTc/QTf of > 60 msec from the post antiemetic ECG in either the native rhythm or paced rhythm will be used as a criteria for an adverse event and would be graded as a grade 3 adverse event.
- Ventricular arrhythmia: VT (≥ 3 beats in a row) or VF.
- Sinus tachycardia (pulse >140/min after recumbency).
- Heart rate is > 120 bpm with > 20 bpm increase from previous evaluation.
- New occurrence of atrial dysrhythmias (SVT, atrial fibrillation, or atrial flutter).
- Abnormal ST and/or T-wave changes including ST depression of ≥ 2 mm (as measured from isoelectric line to the ST segment at a point 60 msec at the end of the QRS complex); T-wave inversion of ≥ 4 mm (measured from isoelectric line to peak of T-wave) as long as the main QRS vector is positive.
- Ventricular tachycardia, including Torsade de Pointes.

See **Table 5** in Section 9 for recommended dose reductions, etc., in the above situations.

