# 6.3 Subject Exclusion Criteria

- a) Patients who have a standard curative option for their lymphoid malignancy at current state of disease are excluded. For eligibility on this trial, allogeneic stem cell transplantation is not to be considered a standard curative option.
- b) Any serious medical condition, laboratory abnormality, or psychiatric illness that would prevent the subject from signing the informed consent form.
- c) Pregnant females. (Lactating females must agree not to breast feed while taking carfilzomib, lenalidomide or romidepsin).
- d) Known hypersensitivity to thalidomide.
- e) The development of erythema multiforme if characterized by a desquamating rash while taking thalidomide or similar drugs.
- f) Prior use of lenalidomide if discontinued due to toxicity.
- g) Prior therapy with romidepsin if discontinued due to toxicity.
- h) Prior therapy with carfilzomib if discontinued due to toxicity.
- i) Prior therapy with a proteasome inhibitor if discontinued due to toxicity.
- j) Concurrent use of other anti-cancer agents or treatments.
- k) Known seropositive and requiring anti-viral therapy for human immunodeficiency virus (HIV), hepatitis B virus (HBV) or hepatitis C virus (HCV).

- I) Concurrent malignancy requiring active therapy.
  - Patients with more than one type of lymphoma may be enrolled after discussion with the MSK Principal Investigator.
- m) Known central nervous system or meningeal involvement (in the absence of symptoms investigation into central nervous system involvement is not required).
- n) The following known cardiac abnormalities:
  - 1. Congenital long QT syndrome.
  - QTc/QTf interval ≥ 480 milliseconds; unless secondary to pacemaker or bundle branch block.
  - 3. Myocardial infarction within 6 months of cycle one, day one (C1D1). Subjects with a history of myocardial infarction between 6 and 12 months prior to C1D1 who are asymptomatic and have had a negative cardiac risk assessment (treadmill stress test, nuclear medicine stress test, or stress echocardiogram) since the event may participate.
  - 4. Other significant ECG abnormalities including 2nd degree atrioventricular (AV) block type II, 3rd degree AV block.

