#### 10.6 Electrocardiograms

An ECG must be performed within 1 hour (after administration of antiemetic premedication) prior to romidepsin and after completion of each romidepsin infusion for cycles 1 and 2. If no QTc/QTf value greater than 480 msec is demonstrated by auto-read or manual read then further ECGs may be omitted for

the duration of study. If a QTc/QTf value greater than 480 but less than 500 msec is encountered then ECGs should be performed within 1 hour prior to romidepsin infusion for the first dose of each subsequent cycle.

If a QTc/QTf is  $\geq$  500 msec is encountered, ECGs should be repeated twice more for a mean of three QTc/QTf values. If the mean is  $\geq$  500 msec, follow dose modification guidelines in **table 6**.

**Note to Investigators:** At the Investigator's discretion, more intensive ECG monitoring can be performed for all romidepsin administrations.

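### Recording only the lesser of QTc and QTf holds recorded values at or below any single formula, lets the formula change between ECGs, and conflicts with the alert trigger it sits under

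*Combined protocol and SAP*

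**What the plan says.** Section 10.5 (Cardiac Alert Findings) lists findings to be reported as AEs or SAEs. The first is "QTc or QTf is ≥ 500 msec". Directly beneath it stands the recording rule: "Either QTc or QTf formulas can be used; the lesser of the two values will be recorded".

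Under the same bullet, for patients with a known bundle branch block, "a change in QTc/QTf of > 60 msec from the post antiemetic ECG will be used as criteria" for an adverse event, graded 3. A parallel rule covers patients with a pacemaker. Neither rule requires the same formula at both time points.

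Other sections use the two labels interchangeably:
- Section 10.6 requires an ECG within 1 hour before romidepsin and another "after completion of each romidepsin infusion for cycles 1 and 2". When a value of 500 msec or more is met, "ECGs should be repeated twice more for a mean of three QTc/QTf values".
- Section 10.6 also decides whether ECGs continue: "If no QTc/QTf value greater than 480 msec is demonstrated by auto-read or manual read then further ECGs may be omitted for" the rest of the study.
- Section 6.3 excludes patients with a "QTc/QTf interval ≥ 480 milliseconds; unless secondary to pacemaker or bundle branch block".
- Table 5 (section 9.5.2, romidepsin and cardiac toxicity) compares QTc/QTf with baseline, but its criterion is an absolute 500 msec.

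No section defines QTc, fixes one formula per patient or for reporting, or asks for both values, the uncorrected QT with heart rate, or the formula used. The manual read that section 10.5 requires for alerts does not settle the formula either.

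**The concern.** Three features of the rule cause difficulty.

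1. **One-sided selection.** Whichever formula is later taken as the reference, the recorded value can only equal it or fall below it.
2. **Formula switching.** Which correction is smaller depends on heart rate, so two ECGs from one patient can be recorded on different scales. A change score or a mean of three values needs one scale.
3. **Internal conflict.** The trigger is worded so that either value at 500 msec is enough, whereas a recorded lesser value reaches 500 only if both do. In addition, allowing either formula permits a site to compute one value, whereas taking the lesser requires two. Sites in this multicenter trial could reasonably act differently.

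What is at stake is the classification of a few events. Safety is the primary endpoint. QT alerts are reported as AEs or SAEs. The change of more than 60 msec is graded 3, and section 9.3.2 counts non-hematologic toxicity of grade 3 or higher attributed to study drugs as a DLT. DLTs in cycles 1 to 4 feed the phase IIa stopping rule in section 14.0 (at least 3 of the first 6, at least 6 of the first 12, or more than 10 of 20). With counts that small, the class of a single event can matter.

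**Working it through.** The plan states no figure that depends on the QT formula, so there is nothing to reproduce. The check covers direction, size, switching and change scores.

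**Direction (no assumption needed).** For any two values A and B, min(A, B) ≤ A and min(A, B) ≤ B. The recorded value is never above either formula.

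**Size at a single ECG.** Assumption: QTc is Bazett, QT/RR^(1/2), and QTf is Fridericia, QT/RR^(1/3), with RR = 60/HR. Then Bazett/Fridericia = RR^(1/3 − 1/2) = (HR/60)^(1/6). Below 60 bpm Bazett is the smaller, above 60 Fridericia is, and at 60 they agree.

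| HR (bpm) | Ratio | One formula gives 500 | Recorded |
|---|---|---|---|
| 45 | 0.953 | Fridericia | 500 × 0.953 = 477 |
| 50 | 0.970 | Fridericia | 500 × 0.970 = 485 |
| 55 | 0.986 | Fridericia | 500 × 0.986 = 493 |
| 60 | 1.000 | both | 500 |
| 70 | 1.026 | Bazett | 500 / 1.026 = 487 |
| 90 | 1.070 | Bazett | 500 / 1.070 = 467 |

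**Average shift.** This is a simulation, and none of its inputs comes from the documents: Fridericia QT with mean 430 and SD 25 msec; heart rate with the mean and SD shown, limited to 40–140 bpm.

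| Mean HR (SD) | Recorded minus all-Fridericia | Recorded minus all-Bazett |
|---|---|---|
| 60 (10) | −5.1 msec | −4.4 msec |
| 70 (12) | −1.7 | −12.0 |
| 80 (12) | −0.3 | −20.7 |
| 90 (15) | −0.2 | −29.3 |

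At mean 70 bpm, the share of ECGs at or above 500 msec is 1.9% by Bazett, 0.25% by Fridericia and 0.21% by the lesser of the two.

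**Switching within a patient.** Section 10.6 gives 2 cycles × 2 infusions × 2 ECGs (before and after) = 8 per patient. Taking the SDs above as between-patient and adding a within-patient heart-rate SD of 8 bpm (also assumed), the share of patients whose 8 ECGs fall on both sides of 60 bpm is 70%, 49%, 25% and 11% for mean heart rates of 60, 70, 80 and 90. Because the formulas agree at 60 bpm, crossing it causes no jump. The discrepancy grows with distance from 60, and at 55 bpm it is about 7 msec.

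**Change criterion.** Take a Fridericia rise of 65 msec, from 420 to 485.
- HR 85 to 55: the pre-dose value is recorded by Fridericia as 420. The post-dose value is recorded by Bazett as 485 × 0.9856 = 478. The recorded change is 58, below the criterion. Bazett throughout would give 33.
- HR 55 to 90: the pre-dose value is recorded by Bazett as 420 × 0.9856 = 414. The post-dose value is recorded by Fridericia as 485. The recorded change is 71. Bazett throughout would give 105.

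The recorded change can therefore err in either direction. In both examples it matches neither single-formula answer.

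**The case against.** The strongest reply is that the rule is close to Fridericia recording in practice. Under the Bazett/Fridericia assumption the lesser value is Fridericia at every heart rate above 60 bpm, and the average shift against all-Fridericia is then 2 msec or less at mean rates of 70 to 90. The drop from 500 to 467 at 90 bpm is simply the gap between the formulas. It represents lost events only if Bazett is the reference, and nothing in the documents says so. Taking the lesser value may also be a deliberate guard against over-correction at fast rates. All of this stands as to size. It would justify choosing one formula, but not a rule that changes formula with heart rate.

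A reader might infer that the trial's primary safety data are biased, or that a QT change-from-baseline analysis is distorted. The documents do not support either. Section 14.0 plans no QT table and no QT change analysis, and QT is not a named endpoint. The criterion of more than 60 msec covers only bundle branch block and pacemaker patients and refers to the post-antiemetic ECG. For everyone else the criterion is an absolute 500 msec.

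Two further limits stand. The recording sentence sits under the 500 msec alert, so carrying it over to the 480 msec rules is inference. And the claim that an alert is logged only when both formulas reach 500 is one reading; the trigger itself can be read as met by either.

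**Conclusion.** The point holds as a minor, inexpensive correction. Three things follow from the text alone: recorded values cannot exceed those of any single formula, no formula is fixed, and the trigger and the recording rule conflict. Every size given rests on QTc meaning Bazett and QTf meaning Fridericia, and the averages also rest on the assumed heart-rate and QT distributions.

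On those assumptions the effect is small against Fridericia at usual rates. It is larger in bradycardia (15 msec at 50 bpm, 23 at 45) or against Bazett. The practical exposure is the classification of a 500 msec event, or of a grade 3 change in a bundle branch block or pacemaker patient that could become a DLT if attributed to study drug. The documents do not give the number of such patients or their heart rates, so no count of affected events can be stated. General under-counting of QT events is not shown.

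**What to change.** - At each ECG, record both corrected values, or the uncorrected QT and heart rate from which either can be derived.
- State which correction QTc denotes.
- Name one formula, used at both time points of any change and for all three values of any mean, for AE reporting and any QT summary.
- Ask the clinical team to reconcile the either-value trigger with the lesser-value recording rule in section 10.5, and to say whether the recording rule extends to the 480 msec rules in sections 6.3 and 10.6. No threshold or dose rule is proposed here.

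The likely cost is one or two eCRF fields and a sentence or two of protocol text. The eCRF is not among the documents, so this is an estimate; if QT and heart rate are already captured, only the text changes. Sites now computing one value would need the second, which comes from the same tracing. The reported QT event count may rise slightly. For patients already treated, section 16.3.4 has participating sites keep source documents for 7 years after closure, so re-derivation may be possible if the tracings are among them.

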#### 10.6 Electrocardiograms

An ECG must be performed within 1 hour (after administration of antiemetic premedication) prior to romidepsin and after completion of each romidepsin infusion for cycles 1 and 2. If no QTc/QTf value greater than 480 msec is demonstrated by auto-read or manual read then further ECGs may be omitted for

the duration of study. If a QTc/QTf value greater than 480 but less than 500 msec is encountered then ECGs should be performed within 1 hour prior to romidepsin infusion for the first dose of each subsequent cycle.

If a QTc/QTf is  $\geq$  500 msec is encountered, ECGs should be repeated twice more for a mean of three QTc/QTf values. If the mean is  $\geq$  500 msec, follow dose modification guidelines in **table 6**.

**Note to Investigators:** At the Investigator's discretion, more intensive ECG monitoring can be performed for all romidepsin administrations.

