# 9.5.2 Romidepsin Dose Modification in Case of Cardiac Toxicity

The guidelines for cardiac monitoring and timing of ECG assessments are presented in Table 5. Prolongation of  $QTc/QTf \ge 500$  msec is considered to be an alert associated with romidepsin administration.

Table 5: Dose alteration based on cardiac abnormalities					
Parameter/Symptoms	Change	Action	Dosing/ Continuation		
Sinus tachycardia	Pulse >140/min after recumbency	Hold further dosing and treat appropriately. If	If resolved, restart romidepsin at reduced dose as per table 3. If not resolved, take off study.		
Atrial dysrhythmia (SVT, atrial fibrillation, or atrial flutter)	New occurrence	desired, a local cardiologist may be consulted.			
Prolongation of QTc/QTf compared to baseline	To ≥500 msec				
Heart rate	> 120 bpm with > 20 bpm increase from previous evaluation;				
Ventricular tachycardia	≥3 beats in a row				
Ventricular fibrillation; Torsade de Pointes	New occurrence	Hold further dosing and treat appropriately. The MSK PI should be notified immediately and local cardiologist should be consulted.	Hold further dosing until MSK PI and cardiologist evaluation is complete		
A subsequent episode above, despite dose red	_	Take off study			
T-wave morphology	Inversion of ≥4 mm a	Hold further dosing and treat appropriately. If desired, a local cardiologist may be consulted.	If resolved, restart romidepsin at reduced dose of 10 mg/m² In some patients, ST segment and T-wave morphology changes may recur despite a dose reduction to 10mg/m². In such cases, further treatment should be held until the ECG changes resolve. If the patient experiences no concomitant clinical events, treatment may be resumed at the reduced dose of 10 mg/m² If not resolved, take off study		
ST-segment	Depression of ≥2 mm b				

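### The response to a QTc/QTf of 500 msec or more is written inconsistently in Table 5, Section 10.5 and Section 10.6, and the ECG value to be graded is not stated

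*Combined protocol and SAP*

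**What the plan says.** Three places govern a QTc/QTf at or above 500 msec.

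- **Table 5** (Section 9.5.2, Romidepsin Dose Modification in Case of Cardiac Toxicity) has a row "Prolongation of QTc/QTf compared to baseline" with a change to 500 msec or more. The action printed against this group of rows is to hold dosing and treat, and then: "If resolved, restart romidepsin at reduced dose as per table 3. If not resolved, take off study". A further episode despite dose reduction is listed as a reason to come off study. Repeat ECGs and averaging are not mentioned.
- **Section 10.5** (Cardiac Alert Findings) makes the same value an alert, reportable as an AE or SAE. On confirmation it says "All alerts must be confirmed via manual read of the patients ECG; the machine reading alone is not adequate". On the value it says "Either QTc or QTf formulas can be used; the lesser of the two values will be recorded". On the action it says "the individual decision about a delay of administration, dose reduction, or withdrawal from the study will be made by the Investigator". It closes by referring to Table 5 "in Section 9 for recommended dose reductions, etc., in the above situations".
- **Section 10.6** (Electrocardiograms) says that after a reading of 500 or more "ECGs should be repeated twice more for a mean of three QTc/QTf values". If the mean is 500 or more, the site is to "follow dose modification guidelines in" Table 6. In this protocol Table 6 is the Study Evaluation Schedule in Appendix G. Footnote 2 of that schedule places the romidepsin dose modifications in Table 5.

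The DLT definition (Section 9.3.2) counts attributed non-hematologic toxicity of grade 3 or more, and inability to receive day 1 of cycle 2 because of continuing drug-related toxicity. Section 14.0 uses DLTs in cycles 1-4 for the phase IIa stopping rule.

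**The concern.** The trial runs at more than one center, and the safety and toxicity profile is a primary endpoint. If the trigger for holding romidepsin depends on the page a site follows, the same tracings can lead to a hold and reduced restart at one site and no dose change at another. Because Table 5 also provides for removal from study, the choice can decide whether a patient stays on treatment, and so the exposure over which toxicity is described.

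A second gap concerns the data. Adverse events are graded with CTCAE v4.0 as a guide, but nothing says whether the graded value is the single manual read, the mean of three, or the lesser of QTc and QTf. Without that, QTc toxicity may not be tabulated in the same way for every patient.

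**Working it through.** The plan states no figure to reproduce here. The check is a comparison of the texts, a worked example, and an illustration of frequency.

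**1. The three texts side by side**

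| | Table 5 | Section 10.5 | Section 10.6 |
|---|---|---|---|
| Value used | One value, 500 or more | Manual read; lesser of QTc and QTf recorded | Mean of three, 500 or more |
| Repeats | None mentioned | None mentioned | Two more ECGs |
| Action | Hold; reduced restart or off study | Investigator decides; Table 5 recommended | Dose modification if the mean qualifies |
| Table cited | Table 3 for the reduced dose | Table 5 | Table 6 (visit schedule) |

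Table 5 and Section 10.5 never refer to the mean. The one sentence in Section 10.6 that could tie the mean to Table 5 names a table with no dose rule.

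**2. Worked example**

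Readings 505, 490, 492: mean = (505 + 490 + 492) / 3 = 1487 / 3 = 495.7.

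- Table 5: the first value is at least 500, so the row is met.
- Section 10.6: 495.7 is below 500, so no dose modification follows. The readings between 480 and 500 still bring an ECG before the first dose of each later cycle.
- Section 10.5: once the first reading is confirmed manually it is reportable, and the action is the investigator's.

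Readings 520, 495, 490: mean = 1505 / 3 = 501.7. Both numeric rules are met, so the rules do not always disagree.

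**3. How often the single value and the mean would split (illustration only)**

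Assumptions, none of them in the documents: the three readings are independent and normal with true value μ and within-patient SD σ of 5, 10 or 15 msec; the mean includes the first reading; the lesser-of-two rule is ignored.

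P(mean < 500 | first ≥ 500) = ∫ from 500 to ∞ of (1/σ) φ((x − μ)/σ) · Φ((1500 − x − 2μ)/(σ√2)) dx, divided by 1 − Φ((500 − μ)/σ).

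| True QTc μ | σ = 5 | σ = 10 | σ = 15 |
|---|---|---|---|
| 490 | 0.99 | 0.84 | 0.69 |
| 495 | 0.84 | 0.60 | 0.50 |
| 500 | 0.30 | 0.30 | 0.30 |
| 505 | 0.02 | 0.10 | 0.15 |
| 510 | <0.01 | 0.02 | 0.06 |

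Check at μ = 500: the first reading and the mean have correlation 1/√3, so the probability is arccos(1/√3)/π = 0.955/3.142 = 0.30 for any σ, as tabulated.

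The result depends almost entirely on where the true QTc lies. These are also rates among first readings of 500 or more. At μ = 490 such a first reading occurs with probability only 0.02, 0.16 and 0.25 for the three SDs.

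**4. Link to the DLT count**

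No DLT criterion in Section 9.3.2 mentions the cardiac hold, Table 5 or a mean QTc. Two indirect routes exist: the grade assigned to an attributed QTc event, and a hold for continuing toxicity that prevents day 1 of cycle 2. The only QTc grade given in the text is grade 3 for a change of more than 60 msec in patients with bundle branch block or a pacemaker. The CTCAE cut-offs are not reproduced, so whether a given tracing is grade 3 cannot be settled from the documents.

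**The case against.** The strongest answer is that the passages form one sequence: Section 10.5 confirms and reports the alert, Section 10.6 repeats the ECG and decides whether dose modification is needed, and Table 5 gives the modification. On this view Table 5's silence about repeats is not a contradiction, Table 6 is an obvious slip for Table 5, and the word recommended in Section 10.5 already makes Table 5 guidance to the investigator.

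Much of this stands. Reporting an alert under Section 10.5 while leaving the dose unchanged under Section 10.6 is no conflict, because they are separate acts. The intended table is recoverable from Section 10.5 and calendar footnote 2. But the sequence is the reader's construction. Section 10.5 has its own confirmation step, Table 5 does not refer to Section 10.6, and Table 5's wording on coming off study sits uneasily with a decision left to the investigator.

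A reader might also infer three stronger claims that the documents do not support.

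- That the conflicting wordings decide whether an ECG counts as a DLT. No DLT criterion cites any of them, and the grade cut-offs are absent.
- That Table 5 is mandatory. Section 10.5 calls it recommended; its status is part of what is unclear.
- That the rules disagree on most alerts. That follows only if the true QTc is assumed to lie just below 500; at and above 500 the rate falls to about 30% and lower.

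**Conclusion.** The inconsistency is real but limited. A single value of 500 msec or more meets the Table 5 row, while Section 10.6 calls for dose modification only on a mean of three, and Section 10.5 leaves the action to the investigator. Two sites reading the text in good faith could treat the same tracings differently. The protocol also leaves open which ECG value is graded. This finding rests on the wording alone and does not need the frequency illustration, which shows only that the split can range from nearly none to nearly all of first alerts as the assumed true QTc moves from 510 to 490. The effect on the number of DLTs cannot be quantified from the documents. It is a clarification that should be made, because it touches an operative safety rule and the recording of a primary safety endpoint.

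**What to change.** Reconcile Table 5, Section 10.5 and Section 10.6 as follows.

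1. State one ECG value (single manual read or mean of three, and how the lesser of QTc and QTf enters it) that defines entry to Table 5 and the value graded as an adverse event.
2. State whether Table 5 is binding or a recommendation to the investigator, and make its wording on removal from study agree with that.
3. In Section 10.6, correct the Table 6 reference to Table 5, the table that Section 10.5 and calendar footnote 2 name.

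Which rule applies is for the clinical team. The cost is protocol wording only: Section 10.6 already calls for the repeat ECGs, and no sample size or analysis changes. If tracings have already been graded, record which value was used so that the toxicity tables can be read consistently.
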